# Statistical methods Intention to treat (ITT) analysis will be undertaken to compare treatment effects between groups. Multi-level models will be used to handle any missing outcome measures. Chi-square test will be used for dichotomous or categorical data and ANOVA test will be used for continuous variable. Adjustment will be made for baseline co-variables as appropriate using multiple regression models. Cost per quality adjusted life year (QALY) will be estimated.

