### **Primary endpoint:**

Percentage of patients who hit the therapeutic target at end of year 2 (SUA <360 µmol/L)

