### **STATISTICS**

### Methods

The trial statistician ([name]) will oversee the data management, evaluation and analyses. The database will be developed in collaboration with the CTU using access and analysed using SPSS. SUA will be analysed at baseline, 12 months and 24 months. Comparison will be undertaken between the nurse led intervention and control at each observational point. There will be no interim analyses for efficacy or safety. Intention to

Page **19** of **29** Final version 8 –18 May 2015

treat (ITT) analysis will be undertaken to compare treatment effects between groups. Multilevel models will be used for any missing outcome measures. Chi-square test will be used for dichotomous or categorical data and ANOVA test will be used for continuous variables. Adjustment will be made for baseline co-variables as appropriate. Cost per QALY will be estimated from the SF6D and the direct and indirect costs related to gout and its management.

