### Procedures for missing, unused and spurious data

If participants leave the study for any reason or if there are omitted data we will use multilevel models for any missing outcome measures and an intention to treat (ITT) analysis.

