# A community based randomised controlled trial comparing nurse-led intervention with standard care

# -Analysis plan

Synopsis of the design: A 2 year community based randomised controlled trial will be undertaken in Nottingham to investigate clinical effectiveness and cost-effectiveness of a nurse-led quality of care intervention versus standard of care control. A questionnaire survey will be undertaken in the GP practices in Nottinghamshire to obtain 724 patients with gout according to the American College of Rheumatology (ACR) criteria and at least one acute attack in the past year. They will be randomly allocated to the intervention and the control group using stratified (according to the participated GP practices), block (fixed block of 4 for random allocation to keep the balance between the groups) randomisation method. Participants will be examined at baseline, 12 months and 24 months for outcomes such as serum uric acid (SUA), number of acute attacks in the previous year and quality of life (QoL) (SF36).

Principles of analysis: Intention to treat (ITT) analysis will be conducted. Descriptive analysis on raw differences between groups at baseline, 12 months and 24 months will be undertaken. Multi-level regression model (MLM) will be used for the overall comparison of the treatment effect between groups with repeated measures and missing data. We shall include all data from 3 time points in the same model, with repeated measures as level 1 units and individuals as level 2 units. The treatment group and time points will be considered as covariates in the model together with covariates at baseline for the adjustment purpose. Continuous data (eg, SUA, QoL score, etc) will be analysed using MLM linear regression, whereas dichotomous and categorical data will be analysed using MLM logistic or multinomial models. Comparison will be made between the intervention and the control in the RCT, as well as between the control in the RCT and the observational group.

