# **Outcome measures:**

- 1. Primary outcome: % patients hitting the therapeutic target (SUA≤ 360 μmmol/l) is the primary outcome of the trial. We will examine
  - % patients reaching the target at baseline, 12 months and 24 months within each group
  - % patients reaching the target at baseline, 12 months and 24 months between groups
  - Mean SUA at baseline, 12 months and 24 months within each group
  - Mean SUA at baseline, 12 months and 24 months between groups
  - Mean change of SUA from baseline to 12 months and 24 months within each group
  - Mean change of SUA from baseline to 12 months and 24 months between groups We will also calculate the number needed to treat (NNT) for % patients reaching the therapeutic target SUA less than 360  $\mu$ mol/l, as appropriate.

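### No single primary analysis or effect measure is fixed for the 24-month urate target: chi-square in the protocol, a subject-specific multi-level logistic model in the analysis plan, and an NNT with no stated derivation

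*Supplement*

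**What the plan says.** **Protocol (version 8).** The Primary endpoint section gives "Percentage of patients who hit the therapeutic target at end of year 2", and the Assessment of Efficacy section repeats it as a percentage in each group. Under Statistics, Methods: "Chi-square test will be used for dichotomous or categorical data and ANOVA test will be used for continuous variables". Multi-level models come in for missing data: "If participants leave the study for any reason or if there are omitted data we will use multilevel models for any missing outcome measures". The synopsis adds regression adjustment: "Adjustment will be made for baseline co-variables as appropriate using multiple regression models".

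**Analysis plan.** Under Principles of analysis, the multi-level regression model "will be used for the overall comparison of the treatment effect between groups with repeated measures and missing data". Its structure is given as "with repeated measures as level 1 units and individuals as level 2 units", and for binary outcomes "dichotomous and categorical data will be analysed using MLM logistic or multinomial models". All three visits, baseline included, enter one model. Group, time point and baseline variables are the covariates, and no group-by-time term is stated. Raw between-group differences at each visit are described as descriptive. Under Outcome measures, the primary outcome is the percentage at target, listed within and between groups at each visit, and then: "We will also calculate the number needed to treat (NNT) for % patients reaching the therapeutic target".

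Neither document says which analysis is primary, which effect measure is reported, or how the NNT is obtained.

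**The concern.** Two different analyses of the primary endpoint are prespecified with no order between them. The chi-square works on the percentages themselves. A two-level logistic model with a random effect per person gives a treatment coefficient that compares the odds of being at target for a person with a given random effect. Because the logistic link is non-linear, that coefficient lies further from zero than the log odds ratio for the group percentages, by an amount that grows with the between-person variance. It answers a different question from the stated endpoint. Placing it on a control percentage to obtain an NNT would give the wrong number.

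At stake is the headline result. An odds ratio from the model, a raw difference in percentages and an NNT could appear side by side, on different scales and with different handling of missing visits. The choice of lead result would remain open after the data are seen.

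**Working it through.** The documents give no odds ratio, between-visit correlation or NNT, so there is no planned figure to reproduce. The size can be bracketed from their percentages.

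**Inputs.**
- Protocol, Power calculations: 30% of surveyed patients were on urate-lowering therapy (ULT). SUA was above target in 23% of those on ULT and 75% of those not on it, so about 77% and 25% were at target.
- Protocol, Background: 92% at target after one year in phase 1.
- Assumed: control patients resemble the survey mix; 75% as a more modest nurse-arm result; latent between-visit correlation ρ of 0.1, 0.3 or 0.7.

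**Step 1: marginal quantities at 24 months.** Control: 0.30 × 0.77 + 0.70 × 0.25 = 0.406, odds 0.406/0.594 = 0.6835.
- Nurse 92%: difference 0.514, NNT 1/0.514 = 1.9, marginal odds ratio (0.92/0.08)/0.6835 = 16.8.
- Nurse 75%: difference 0.344, NNT 1/0.344 = 2.9, marginal odds ratio (0.75/0.25)/0.6835 = 4.4.

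**Step 2: conditional odds ratio with a correct 24-month contrast.** The random-intercept variance is σ² = [ρ/(1−ρ)] × π²/3. For each arm, solve p = ∫ expit(η + σz) φ(z) dz for η by Gauss-Hermite integration. The conditional odds ratio is exp(η₁ − η₀). Example, ρ = 0.3: σ = 1.19, η₀ = −0.487, η₁ = 2.977 for 92%, so exp(3.464) = 31.9 and 31.9/16.8 = 1.9.

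| ρ | σ | 75%: conditional OR | ratio to 4.4 | 92%: conditional OR | ratio to 16.8 |
|---|---|---|---|---|---|
| 0.1 | 0.60 | 4.9 | 1.1 | 20.2 | 1.2 |
| 0.3 | 1.19 | 6.5 | 1.5 | 31.9 | 1.9 |
| 0.7 | 2.77 | 19.9 | 4.5 | 224 | 13.3 |

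The percentages are identical down each column. Averaging each model over its random effect returns 0.344 and 0.514 exactly.

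**Step 3: NNT without averaging.** For 75% at ρ = 0.3, placing the conditional odds ratio on the control odds gives 6.5 × 0.6835 = 4.44, a percentage of 4.44/5.44 = 0.82, and an NNT of 1/(0.817 − 0.406) = 2.4 instead of 2.9. At ρ = 0.7 the same step gives 1.9.

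**Step 4: the model as written.** Take control at 40.6% at all three visits, and nurse care at 40.6% at baseline and the higher figure at 12 and 24 months. Fit group plus time with a random intercept by maximum likelihood to the expected outcome patterns.

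| True σ | 92%: group OR (marginal 16.8) | 92%: standardised 24-month difference (true 0.514) | 75%: group OR (marginal 4.4) | 75%: standardised difference (true 0.344) |
|---|---|---|---|---|
| 1 | 5.8 | 0.33 | 3.1 | 0.23 |
| 2 | 8.7 | 0.33 | 4.4 | 0.23 |
| 3 | 12.7 | 0.33 | 6.3 | 0.23 |

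A single group effect must cover baseline, where the arms are equal, as well as follow-up. In the 92% case the fitted model implies about 22% v 58% at baseline, although both arms are at 40.6%. The 24-month difference is diluted, and an NNT standardised from this model would be about 1/0.33 = 3.0 instead of 1.9.

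**The case against.** The strongest reply is that the plan already contains what is needed. The percentage at target is compared between groups at 24 months under the primary outcome, and the NNT is promised for that percentage, so the natural reading takes it from the percentages. A chi-square is a test and fixes no effect measure. The protocol itself provides for multi-level models and regression adjustment, so the analysis plan may be read as extending it. The terms odds ratio and random intercept appear nowhere. A multi-level logistic model is a valid analysis of repeated binary data, and under a correct 24-month contrast its null hypothesis is the same as the marginal one.

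Much of this stands, and it rules out three stronger readings.

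- A reader might infer that the plan cannot deliver its NNT. It can, from the listed percentages or by averaging the model. What is missing is a statement of which.
- A reader might infer that the reported effect will be overstated several-fold. That requires a high between-visit correlation, which the documents do not give, and a group-by-time term, which they do not state. It concerns the odds-ratio scale only. As written, the model can err in the other direction.
- A reader might infer that the analysis plan ignores the percentage endpoint. It does not, but it labels the raw differences descriptive and gives the overall comparison to the model.

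The reply does not remove the gap: no primary analysis or effect measure is named. A random effect per person is an inference, though it is the ordinary meaning of individuals at level 2.

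**Conclusion.** The point holds as a gap in specification for the primary endpoint. The protocol and the analysis plan assign different analyses, neither is named primary, and the model's coefficient is not on the scale of the stated endpoint or the planned NNT.

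The size depends on matters the documents leave open. With a correct 24-month contrast, the conditional odds ratio is about 1.1 to 1.2 times the marginal one at ρ = 0.1, 1.5 to 1.9 times at 0.3, and 4.5 to 13 times at 0.7. With group and time terms only, the standardised 24-month difference falls to about 0.33 against 0.51, or 0.23 against 0.34. The net direction of error is therefore not established. These figures rest on a normal random intercept, the survey's treatment mix for control patients, the assumed correlations, and nurse-arm results of 92% (from a one-year phase 1 study) or 75% (assumed).

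**What to change.** State one primary estimate in both documents: the between-group difference in the percentage at SUA target at 24 months, with a 95% confidence interval.

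1. Fit the multi-level logistic model with a group-by-time term, so that the 24-month contrast is estimated directly. Averaging a model without that term would carry the dilution through.
2. Obtain the difference by marginal standardisation, averaging predicted probabilities over the random effect and the covariates. Name the method for the confidence interval.
3. Derive the NNT and its interval from that difference.
4. Report the chi-square on observed cases as supportive, and label any random-intercept odds ratio as conditional on the individual.

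The cost is a few sentences in each document and one post-estimation step. The protocol names only SPSS, so the plan should say which procedure will do the averaging. No data collection or trial conduct changes.

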# **Outcome measures:**

- 1. Primary outcome: % patients hitting the therapeutic target (SUA≤ 360 μmmol/l) is the primary outcome of the trial. We will examine
  - % patients reaching the target at baseline, 12 months and 24 months within each group
  - % patients reaching the target at baseline, 12 months and 24 months between groups
  - Mean SUA at baseline, 12 months and 24 months within each group
  - Mean SUA at baseline, 12 months and 24 months between groups
  - Mean change of SUA from baseline to 12 months and 24 months within each group
  - Mean change of SUA from baseline to 12 months and 24 months between groups We will also calculate the number needed to treat (NNT) for % patients reaching the therapeutic target SUA less than 360  $\mu$ mol/l, as appropriate.

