### **Secondary endpoints:**

Percentage with reduction of frequency of acute attacks in the second year. Difference in QOL scores for SF36 and GAQ at end of study.

Percentage with reduction in size of the largest index tophus and reduction in number of tophi.

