### TRIAL / STUDY TREATMENT AND REGIMEN

The total study duration will be 3 years (8 month recruitment period, 2 years participation, 4 months analysis and writing up).

All appointments with our research nurses will be at the participants' local GP practice or in the participants' own home.

The study regimen is summarised in the table below (see also appendix1):

	RCT – nurse	RCT – control/
	intervention	standard care arm
Enquiry: age, sex, gout history, drug history, family history,	Х	X
comorbidities		
Individualised advice on management of acute attack	X	X
(selecting from ice packs, oral colchicine, oral NSAID plus		
PPI, corticosteroid).		
Provision of Arthritis UK patient booklet.	X	X
Tophi assessment (sites), if present	X	X
A clear verbal explanation of gout	X	
Individualised explanation of relevant risk factors	X	
Individualised advice on ways to reduce uric acid levels by	Х	
lifestyle modification, if appropriate		
Advice on ULT	X	
Height and weight (BMI)	X	X
Baseline/recruitment questionnaire (incl. SF36 & GAQ)	X	X
Serum uric acid, GFR and creatinine	X	X
Diary of acute attacks	X	X
Record of visits to GPs re gout management		X
SF36 'Quality of life' forms during acute attacks	Х	Х
12 month SUA	Х	X
12 month GFR & creatinine	Х	Х
12 month questionnaire (incl. SF36 & GAQ)	Х	X
12 month weight	Х	X

Page **15** of **29** Final version 8 –18 May 2015

24 month bloods	Х	X
24 month questionnaire (inl. SF36, GAQ, joint pain,	X	X
stiffness & function, gout attack triggers)		
24 month blood pressure	X	X
24 month weight	Х	Х

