### **B] Control/Standard Care arm**

Participants randomised to this group will have one consultation appointment with the research nurse. At this appointment they will be assessed by the nurse (identical enquiry, examination and investigations as above) and be provided with the Arthritis Research UK gout information booklet and a diary to prospectively document their acute attacks (frequency, duration, medical advice sought, medications taken, absence from work). The discussion will focus on the management of acute attacks and not on long-term management. In addition, they will be asked to provide a blood sample to check their SUA level at baseline, 12 months and 24 months, and complete a QOL questionnaire at 12 months (a new diary will be given at this point) and 24 months. This standard care group of participants will remain under the care of their general practitioner.

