### **Secondary Efficacy Endpoints:**

Percentage in each group with reduced number of acute attacks in the second year of the study

Quality of life scores (SF36 and GAQ) at end point compared to baseline in each group and comparison of endpoint QOL scores between the two groups.

Reduction in size and number of tophi.

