# 2. Secondary outcomes

- Number of acute attacks in preceding year, year 1 and year 2 within each group and between groups
- Number of patients with tophi at baseline, 12 months and 24 months with each group and between groups
- Mean QoL scores (overall, different domain scores of SF36 and the Gout
   Asssessment Questionnaire (GAQ) including the Gout Impact Scale (GIS) of the GAQ.
   at 0, 12 and 24 months within each group and between groups
- Mean change of QoL scores from baseline to 12 months and 24 months within each group and between groups

**Covariates and baseline predictors:** age, gender, body mass index, disease duration, tophi, associated comorbidity etc.

Task allocation and timetable: The Nottingham CTU will undertake randomisation, development of the database for RCT and the web-based data entry platform. CTU will also conduct data monitoring and quality control for the RCT data. Academic Rheumatology will recruit patients, enter the data through a web-based data entry platform for the RCT data and develop an independent database for the observational group. Both datasets are not open for any interim analysis between baseline and 24 months to keep the randomisation. Analysis will start after 24 months when the data has been fully completed, quality checked over and closed. Analysis for clinical effectiveness (efficacy and side effects) will be completed in 3 months after the closing date of the data. Analysis for cost-effectiveness will be completed in 12 months, as it requires acquisition of additional data for cost. In brief:

- Recruitment 8 months
- RCT and observation 24 months
- Results for clinical effectiveness 3 months
- Results for cost-effectiveness 12 months

Economic Analyses Plan.

Two economic analyses are planned: the first being an economic analysis alongside the RCT and the second modelling the costs and benefits over a longer time horizon. The base case in both models would use an NHS perspective, with a societal perspective (that include indirect costs such as lost productivity) being undertaken in a sensitivity analysis.

Economic analysis alongside the RCT

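### The analysis plan scores the primary endpoint at SUA ≤360 against the protocol's <360, and gives no analysis of tophus size or number, whose follow-up measurement is not clearly scheduled

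*Supplement*

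**What the plan says.** **Primary endpoint.** Protocol version 8, Primary endpoint, gives "Percentage of patients who hit the therapeutic target at end of year 2 (SUA <360" µmol/L. The synopsis (Outcome measures) and the Primary Efficacy Endpoint paragraph use the same strict inequality. The analysis plan, Outcome measures, item 1, gives "patients hitting the therapeutic target (SUA≤ 360". The same item then bases the NNT on patients "reaching the therapeutic target SUA less than 360" µmol/L.

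**Tophus endpoint.** Protocol version 8, Secondary endpoints, gives "Percentage with reduction in size of the largest index tophus and reduction in number of tophi". The Secondary Efficacy Endpoints paragraph repeats it as "Reduction in size and number of tophi". The analysis plan, Secondary outcomes, has a single tophus line: "Number of patients with tophi at baseline, 12 months and 24 months with each group and between groups".

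**Measurement.** The table in the protocol's treatment and regimen section has one tophus row, "Tophi assessment (sites), if present", ticked for both arms. The assessment text under the nurse intervention describes calliper measurement of the longest tophus and recording of the number and sites, with no time point. The control arm section says "Participants randomised to this group will have one consultation appointment with the research nurse" and that the same examination is done there.

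**The concern.** A binary primary endpoint needs one rule, fixed before the data are seen. Here a participant at exactly 360 µmol/L is a failure under the protocol, a success in the plan's primary percentage, and a failure again in the plan's NNT.

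For tophi, the protocol's background section names reduction in size and number among the patient-centred outcomes that the trial is meant to demonstrate. The analysis plan has no line for either. If only prevalence is analysed, the stated endpoint goes unreported. If size and number are analysed anyway, the population, the measure and the handling of controls will be chosen after the data are in. An unclear measurement schedule adds to this, because the nurse arm has repeated visits and the control arm has far fewer contacts.

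**Working it through.** **1. How many participants could the inequality sign affect?**

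Inputs, from the protocol's Power calculations: mean SUA 318 with 23% above 360 on urate-lowering therapy (ULT); mean 434 with 75% above 360 off ULT. The number per arm is 256 (synopsis). Assumptions: SUA is normally distributed, and the two survey groups stand in for the two arms.

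Implied standard deviations:
- on ULT: (360 − 318) / 0.739 = 56.8
- off ULT: (360 − 434) / (−0.674) = 109.7

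The probability of a reported value of exactly 360 on a reporting grid of width w is Φ((360 + w/2 − mean)/SD) − Φ((360 − w/2 − mean)/SD).

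| Reporting grid | On ULT | Off ULT | Risk difference, <360 | Risk difference, ≤360 |
|---|---|---|---|---|
| Whole units (w = 1) | 0.53%, 1.4 of 256 | 0.29%, 0.7 of 256 | 76.73 − 24.86 = 51.9 points | 77.27 − 25.15 = 52.1 points |
| Nearest 10 (w = 10) | 5.3%, 13.7 of 256 | 2.9%, 7.4 of 256 | 74.24 − 23.57 = 50.7 points | 79.58 − 26.47 = 53.1 points |

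The NNT in whole units is 1/0.519 = 1.93 under the strict rule and 1/0.521 = 1.92 under the inclusive rule. On the 10-unit grid it is 1/0.507 = 1.97 and 1/0.531 = 1.88. Power with the protocol's 70 per arm exceeds 99.9% in all four cases. No section says that results are rounded to 10 units; that row only shows the upper end of the range.

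**2. Does tophus prevalence stand in for size and number?**

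| Course of an illustrative participant | Protocol endpoint | Plan's tophus line |
|---|---|---|
| Index tophus halves in diameter, still present | Reduced size | No change |
| Five tophi become one | Reduced number | No change |
| All tophi clear | Reduced size and number | Change |
| No tophi at baseline, one appears | Not a reduction | Change |

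The two agree only when tophi clear completely. The documents give no tophus prevalence, so the number of participants concerned cannot be estimated.

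**3. Is follow-up measurement scheduled?**

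- The tophus row names sites only, not diameter or number, and has no time label.
- SUA and weight appear once unlabelled and again in rows marked 12 or 24 months. Tophi do not reappear.
- The diary, the record of GP visits and the SF36 forms during attacks are also unlabelled, yet all run through follow-up. An unlabelled row is therefore not necessarily baseline only.
- The plan's tophus line covers baseline, 12 and 24 months, between groups, which implies ascertainment in both arms at follow-up.
- Weight and blood pressure at 24 months are ticked for both arms, and the list of protocol changes refers to a final 24-month assessment that participants attend.

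Together these show an intention to record tophus presence at follow-up. They do not clearly schedule diameter and number.

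**The case against.** The strongest reply on the threshold is that it is immaterial. The strict form stands in three places in the protocol and in the plan's NNT sentence, so the single ≤ looks like a slip that echoes the guideline target quoted in the protocol's background. That is fair as to size: about 1 patient per arm, and no effect on power. A reader might infer that results in a treat-to-target arm would cluster at 360 and make the sign matter. The documents do not support this: the background speaks of bringing SUA well below that level, and the surveyed patients on ULT averaged 318. What stands is that the primary rule is written in two ways.

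On tophi, a reader might infer that the endpoint cannot be computed, or that controls have no follow-up data. The documents do not support that either. The tophus row is undated rather than dated to baseline, the plan intends tophus status at 12 and 24 months, controls have 24-month physical measurements, and Appendix 1 of version 8, to which the table refers, is not shown. Nor does the plan say that size and number are dropped. It dates from July 2013, and the May 2015 protocol keeps them. None of this supplies the missing analysis of size and number, or a stated time for the calliper measurement.

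**Conclusion.** The point holds in a limited form. The primary endpoint has two cut-offs, one of them at odds with the plan's own NNT. On the survey figures, with normality and whole-unit reporting assumed, this concerns about 1 participant per arm and moves the risk difference by about 0.2 points. With 10-unit rounding, which is purely an assumption, it would concern about 7 to 14 per arm and 2.4 points. Neither case threatens the primary conclusion.

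The tophus gap is the more substantive part. The protocol's size and number endpoint has no analysis in the plan, and prevalence measures something else. Follow-up measurement of size and number is not clearly scheduled in the visible text. That is a lack of clarity to resolve, not proof that the data will be absent.

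**What to change.** - **Threshold:** use the protocol's <360 µmol/L throughout the analysis plan, for the primary percentage and the NNT alike. This concerns only the scoring of the endpoint.
- **Tophus analysis:** add, among participants with tophi at baseline, the percentage with a reduced index-tophus diameter and the change in number of tophi, compared between groups. The prevalence line can stay as a supplement.
- **Schedule:** label the tophus row as diameter and number at baseline and 24 months in both arms, taken at the existing 24-month assessment. If prevalence at 12 months is kept, state there how it is ascertained in each arm. Check that Appendix 1 agrees.

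The first two changes are wording. The third costs a few minutes of calliper measurement, only for participants with tophi, at a contact where weight and blood pressure are already taken.
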